6.3 Screen Failures

Subjects who sign the ICF but withdraw or are withdrawn from the study before treatment are defined as screen failures. All screen failures should be recorded on the subject master list. Limited information including reason for screen failure will be recorded on the electronic case report form (eCRF) for screen failures. Screen failure subjects may be re-screened at the discretion of the investigator and in consultation with the medical monitor as needed. Any subject who discontinues participation or is withdrawn before receiving a treatment assignment, and who is re-screened at a later time will be assigned a new subject number and recorded as re-screened.

7 STUDY TREATMENT(S)

7.1 Treatments Administered

[figure not shown]
Test articles will be supplied by Paratek Pharmaceuticals, Inc. (the sponsor). Test articles will be labeled according to regulations.

The test articles should be administered only to subjects who have provided pediatric assent (as appropriate per local regulations) and informed consent signed by his/her parent/LAR and who meet all of the inclusion criteria and none of the exclusion criteria. Once the test article has been assigned to a subject, it must not be reassigned to another subject.

Following a Screening period of up to 48 hours, eligible subjects will be assigned a dosing regimen of omadacycline per PI discretion.

[figure not shown]
7.2 Identity of the Investigational Product: Omadacycline

Oral Formulation (Omadacycline)

Administration Please reference Section 7.5

Intravenous Formulation (Omadacycline)

Administration Please reference Section 7.5

7.3 Dose Selection Rationale

The dosing regimen of omadacycline selected for this study is based on the nonclinical and clinical experience to date, including *in vitro* antibacterial activity, PK characteristics and modeling, clinical efficacy in prior studies, the overall safety and tolerability profile, and the FDA approved dosing regimen for CABP and ABSSSI. Based on interim PK and safety analyses, the dose could be modified during the study.

This study will involve a single dose of either 100 mg IV or 300 mg oral omadacycline in a pediatric population in order to establish pediatric dosing as compared to adult subjects.

7.4 Description of Treatments

Subjects will be assigned to a single dose of either 100 mg intravenous omadacycline (in 100 mL normal saline solution) infused over 30 minutes or 300 mg oral omadacycline (150 mg tablet x 2).

Eligible subjects will fall into one of the following treatment groups:

Test Article Administration	Adolescents 12 to < 18 years of age	Children 8 to < 12 years of age
IV Omadacycline	10 pts	10 pts
Oral Omadacycline	10 pts	10 pts

7.5 Test Article Administration

7.5.1 Administration of Oral and IV Treatment

Subjects will receive a single dose of either IV or oral test article on Day 1.

Oral Omadacycline

All doses of oral test article should be taken with water.

All oral doses should be taken in a fasted state. Fasting is defined as no food, antacids, or multivitamins containing multivalent cations (e.g., aluminum, magnesium, calcium, bismuth, iron, or zinc) or drink except water for at least 6 hours before dosing. After dosing, no food is permitted for 2 hours and no dairy products, antacids, or multivitamins containing multivalent cations (e.g., aluminum, magnesium, calcium, bismuth, iron, or zinc) for 4 hours.

IV Omadacycline

Infusion of IV test article in 100 mL normal saline solution will be administered continuously over approximately 30 minutes. Infusion start and stop times are to be recorded in the source documents and on the eCRF.

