This study is being conducted in children and adolescents already hospitalized and already receiving antibacterial treatment. As such, exposure to a single dose of omadacycline is a reasonable added therapy. Study related blood draws can be performed through indwelling catheters already in place. The study assessments following a single dose of omadacycline will be sufficient to characterize the PK of omadacycline and model exposure with multiple doses.

Primary Objective:

To characterize the PK of single intravenous (iv) and oral doses of omadacycline in children and adolescents 8 to < 18 years of age with suspected or confirmed bacterial infections.

Secondary Objective:

To evaluate the safety and tolerability of single iv and oral doses of omadacycline in children and adolescents 8 to < 18 years of age with suspected or confirmed bacterial infections.

Study Design:

This is a Phase 1, open-label, multi-center study in children and adolescent subjects (males and females, 8 to < 18 years of age) with suspected or confirmed bacterial infections who are receiving concomitant systemic antibacterial therapy. This study will consist of 2 age cohorts:

- Cohort 1 (adolescents): 12 to < 18 years of age
- Cohort 2 (children): 8 to < 12 years of age

The study will consist of a Screening period of up to 48 hours prior to dosing, a single dose of study drug on Day 1, and a Study Completion Visit between Days 4-7.

Subjects will undergo screening evaluations to determine eligibility within 48 hours prior to dosing. Approximately 40 subjects (20 per age cohort) will be enrolled to obtain at least 24 PK evaluable subjects (with a minimum of 6 subjects per treatment, per age cohort).

On Day 1, based on Principal Investigator (PI) discretion, subjects will receive either a single dose of 100 mg iv omadacycline (in 100 mL normal saline solution) infused over 30 minutes at room temperature, or they will receive a single dose of 300 mg oral omadacycline tablet (150 mg tablet x 2). Oral study drug will be administered in the morning with no food or drink except for water at least 6 hours prior to dosing. Subjects will have no food or drink except water for at least 2 hours after dosing and no dairy products, antacids, or other aluminum- or calcium-containing products (e.g., vitamins, supplements) for 4 hours after dosing.

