5 INVESTIGATIONAL PLAN

5.1 Overall Study Description

This is a Phase 1, open-label, multi-center study in children and adolescent subjects (males and females, 8 to < 18 years of age) with suspected or confirmed bacterial infections who are receiving concomitant systemic antibacterial therapy. This study will consist of 2 age cohorts:

- Cohort 1 (adolescents): 12 to < 18 years of age
- Cohort 2 (children): 8 to < 12 years of age

The study will consist of a Screening period of up to 48 hours prior to dosing, a single dose of study drug on Day 1 and a Study Completion Visit between Days 4 to 7.

Subjects will undergo screening evaluations to determine eligibility within 48 hours prior to dosing. Approximately 40 subjects (20 per age cohort) will be enrolled.

On Day 1, per Principal Investigator (PI) discretion, subjects will receive a single dose of either intravenous or oral omadacycline. For those receiving intravenous omadacycline, a 100 mg IV dose (in 100 mL normal saline solution) infused over 30 minutes at room temperature will be administered. For those receiving oral omadacycline, a single dose of 300 mg oral omadacycline tablet (150 mg tablet x 2) will be administered.

Oral study drug will be administered in the morning in a fasted state with no food or drink except for water at least 6 hours prior to dosing. Fasting is defined as no food, antacids, or multivitamins containing multivalent cations (e.g., aluminum, magnesium, calcium, bismuth, iron, or zinc) or drink except water for at least 6 hours before dosing. Subjects will have no food or drink except water for at least 2 hours after dosing and no dairy products, antacids, or other aluminum- or calcium-containing products (e.g., vitamins, supplements) for 4 hours after dosing.

A total of 7 blood samples for PK analysis for oral omadacycline and 8 blood samples for iv omadacycline will be collected at specified time points prior to dosing and through 48 hours after dosing. Safety assessments will include monitoring of adverse events (AEs), clinical laboratory test results, vital sign measurements, and physical examination findings.

Subjects will complete a Study Completion visit 4 to 7 days after dose completion. This visit may be performed via telehealth with subject's parent/legal authorized representative (LAR) to review ongoing medications and adverse events if the subject has already been discharged from the hospital before Day 4.

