3. Inability to tolerate oral medication (e.g., nausea, vomiting, diarrhea, or any other condition that might impair ingestion or absorption of oral medication – oral treatment only).
4. Inability to fast for 6 hours prior to dosing and/or 2 hours after dosing (oral treatment only).
5. Pregnant or nursing (breastfeeding) in post-menarche females.
6. History of hypersensitivity or allergic reaction (e.g., anaphylaxis, urticaria, other significant reaction) to any tetracycline (e.g., minocycline, doxycycline, or tigecycline).
7. Any surgical or medical condition that, in the opinion of the investigator, might significantly alter the absorption, distribution, metabolism, or excretion of drugs.
8. Family members of the Investigator or a study center employee.

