9 STUDY ACTIVITIES

The full assessment schedule is presented in the Schedule of Events (see [Appendix 1](#)). Subjects should be seen for all assessments and visits on the designated time and day.

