Assent (as required/permitted)	X ^d									
Inclusion/exclusion criteria	X	X								
Medical history/current medical conditions	X									
Demography	X									
Physical examination ^e	X							X		
Height & Weight	X ^f									
Serum or urine pregnancy test ^g	X									
Vital signs (BP & HR) ^h	X	X			X		X	X		
Temperature	X	X						X		
Hematology	X ⁱ							X		
Serum chemistry	X ⁱ							X		
Study drug administration ^j			X							
PK blood collection		X		X	X	X	X	X	X	
Adverse events ^k	< -----X----- >									
Prior/concomitant medications ^l	< -----X----- >									

Schedule of Assessments – Oral Treatment Arm

Study Phase	Screening ^a	Oral Treatment Period							Study Completion ^b
Study Day	D –2 to D–1	D1				D2	D3	D4-D7	
			Post Dose Timepoint						
Study Hour	–48 hrs.	Pre-dose ^c	0	1 Hr.	2 Hrs.	3 Hrs.	8 Hrs.	24 Hrs.	48 Hrs.

BMI = body mass index, BP = blood pressure, D = study day, HR = heart rate, ICF = informed consent form, PK = pharmacokinetic

^a Screening period of up to 48 hours is permitted.

^b Study completion visit may be performed via telehealth with subject's parent/LAR to review ongoing medications and adverse events if the subject is discharged from the hospital before Day 4.

^c Pre-dose window is defined as after consent and at least 15 minutes prior to study drug administration.

^d Written and signed ICF/assent as applicable must be obtained before any protocol-specific assessment is performed.

^e Full physical examination to be performed at Screening and 24 hours post-dose. Symptom-driven physical exams may be performed at other timepoints as necessary.

^f Both height and weight to be obtained with shoes off.

^g For post-menarchal females of childbearing potential only.

^h Blood pressure to be performed in supine position.

ⁱ Blood samples for hematology and chemistry will be assessed by site's local laboratory. If standard of care laboratory assessments were performed within 24 hours prior to consent/assent, these results may be used for purposes of determining provided they meet protocol requirements for all screening labs. Refer to Section 8.7.

^j Oral study drug will be administered to subjects in the morning with no food or drink except water for at least 6 hours prior to dosing. After oral dosing, subjects will have no food or drink except water for at least 2 hours and no dairy products, antacids, or multivitamins for 4 hours.

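### Around the oral dose, multivalent cations are barred only in antacids and multivitamins, so single-ingredient iron, zinc and similar products are permitted

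*Protocol*

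**What the plan says.** Protocol 7.2 sends the reader to 7.5 for administration ("Administration Please reference Section 7.5"). For the period before the oral dose, 7.5.1 uses the same 6-hour definition as 5.1: "Fasting is defined as no food, antacids, or multivitamins containing multivalent cations (e.g., aluminum, magnesium, calcium, bismuth, iron, or zinc) or drink except water". For the period after it, 7.5.1 says "After dosing, no food is permitted for 2 hours and no dairy products, antacids, or multivitamins containing multivalent cations", the product part lasting 4 hours. Section 7.9 lists antacids and multivitamins with multivalent cations as excluded from 6 h before to 4 h after oral doses. Section 7.10 permits all treatments not specified as prohibited.

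The overview text is worded differently. On food and drink, the Synopsis and 5.1 state: "Subjects will have no food or drink except water for at least 2 hours after dosing". Their product limit is worded more widely than the one in 7.5.1: "no dairy products, antacids, or other aluminum- or calcium-containing products (e.g., vitamins, supplements) for 4 hours after dosing". SAP 3.1 says the same on both. Footnote j of the oral schedule in Protocol Appendix 1 reads "subjects will have no food or drink except water for at least 2 hours and no dairy products, antacids, or multivitamins for 4 hours", and the SAP's oral schedule repeats it.

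AUC and Cmax are among the primary PK endpoints (SAP 3.2.1.1). The oral arm is planned at 10 subjects per age cohort, with at least 6 PK evaluable (Protocol 7.4 and 12.2).

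**The concern.** The restriction is attached to two product types rather than to the cations it names. A multivitamin containing iron is barred near the dose; an iron tablet is not. That does not serve the evident purpose of a rule that lists iron and zinc by name, and 7.10 turns the silence into permission.

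A second weakness is that the post-dose rule is not the same everywhere. The wider class of aluminum- and calcium-containing products appears in the overview text but not in the administration section, the prohibited-therapy section or the schedule footnote, which are the places site staff are likely to consult when giving the dose.

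At stake are the dosing conditions behind oral AUC and Cmax. These are meant to help set pediatric dosing against adults, and interim PK may change the dose (Protocol 7.3). The cells are small, so one child dosed under different conditions carries visible weight in a cell summary.

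**Working it through.** No effect size can be computed, so the check is a comparison of text. Seven places set a product limit after the oral dose. Six of them also set the food and drink rule; 7.9 covers therapies only.

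| Place | Drinks other than water barred for 2 h after dose | Plain calcium or aluminum product barred for 4 h after dose | Single-ingredient iron or zinc barred |
|---|---|---|---|
| Protocol Synopsis | Yes | Yes | No |
| Protocol 5.1 | Yes | Yes | No |
| Protocol 7.5.1 | No | No | No |
| Protocol 7.9 | Not applicable | No | No |
| Protocol Appendix 1, oral, footnote j | Yes | No | No |
| SAP 3.1 | Yes | Yes | No |
| SAP Appendix 1, oral, footnote j | Yes | No | No |
| **Total** | **5 of 6** | **3 of 7** | **0 of 7** |

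The SAP's IV schedule also carries the oral footnote text; it is not counted.

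Combining all sections, with 7.10 as the default, gives the following by product:

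| Oral product | 6 h before dose | 4 h after dose |
|---|---|---|
| Antacid | Barred | Barred |
| Multivitamin with multivalent cations | Barred (5.1, 7.5.1, 7.9) | Barred (7.5.1, 7.9, footnote j) |
| Single-ingredient iron or zinc | Permitted | Permitted |
| Non-antacid magnesium or bismuth | Permitted | Permitted |
| Non-antacid calcium supplement | Permitted | Barred (Synopsis, 5.1, SAP 3.1 only) |

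The calcium row is split because the aluminum/calcium limit is written only for the 4 h after dosing.

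- Open window for iron, zinc and non-antacid magnesium or bismuth: 6 h + 4 h = 10 h.
- Open window for a non-antacid calcium supplement: the 6 h before dosing.
- Weight of one child in an oral cell: 1/10 = 10% at the planned size, 1/6 = 16.7% at the evaluable minimum. This is a share of the cell, not an estimate of bias.

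Neither wording contains the other. Section 7.5.1 names more cations, but only within antacids and multivitamins. The overview text covers more product types after dosing, but only for aluminum and calcium. A site that applies the stricter text at every point still meets no bar on iron or zinc alone.

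**The case against.** The strongest reply is that the protocol is one document. Silence in 7.5.1 does not permit what 5.1 forbids, and a site that follows every section meets every stated rule. This stands for two of the three elements.

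- **Drinks.** A reader might infer that the study lacks a post-dose drink limit. It does not. Five of six places state it, and exclusion criterion 4 requires oral subjects to be able to fast for 2 h after dosing. The dairy bar in 7.5.1 also covers milk. The omission is editorial.
- **Calcium after dosing.** A reader might infer that the deviation status of a plain calcium supplement given within 4 h after the dose depends on the section read. It does not. Section 5.1 is operative text and prohibits it, and 7.10 refers to treatments not specified as prohibited, not to treatments missing from 7.9. Such intake is already a deviation; the fault is that the places most used for dosing do not say so.

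The reply fails for iron, zinc and non-antacid magnesium or bismuth. Applying 5.1 does not help, because its post-dose limit reaches only aluminum and calcium products beyond antacids, and its pre-dose definition names only antacids and multivitamins.

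It can also be said that antacids and multivitamins are a deliberate scope, since 5.1, 7.5.1 and 7.9 agree on them before the dose. That is possible, but the documents give no reason to restrict iron in a multivitamin and not iron alone. A liquid supplement might be argued to count as a drink; a tablet would not. The Investigator's Brochure and package insert, to which the Introduction refers, may say more, but they are not available here.

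Later detection gives partial cover. Section 7.8 records treatments from 72 h before consent and after dosing, and SAP 4.2 allows case-by-case review for the PK population. However, 8.15 asks for start and discontinuation dates, not clock times, and 8.8 records the times of dosing and last food, not of supplements. A same-day entry may not show whether intake fell inside the window.

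**Conclusion.** The point holds as a gap in scope with a lesser problem of consistency. Single-ingredient oral iron or zinc, and non-antacid magnesium or bismuth, are permitted for the full 10 h around the oral dose, and a non-antacid calcium supplement for the 6 h before it, although the plan names these cations as ones to keep away from the dose. The post-dose calcium and aluminum limit is in force but missing from four of seven places. The drink omission is confined to 7.5.1.

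A reader might go on to infer that oral AUC and Cmax will be distorted. The documents do not support that: they give neither the size of any interaction nor the number of children likely to take such products. The counts above describe wording, not bias. The conclusion rests on one assumption, that the rule is meant to keep the named cations away from the dose whatever product carries them. Severity is minor; this is a cheap improvement.

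**What to change.** Use one rule in the Protocol Synopsis, 5.1, 7.5.1, footnote j of the oral schedule in both documents, and SAP 3.1, with its product part also in 7.9:

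- no food or drink except water from 6 h before to 2 h after the oral dose;
- no oral antacids, multivitamins, supplements or medicines with aluminum, magnesium, calcium, bismuth, iron or zinc as an active ingredient, single-ingredient products included, from 6 h before to 4 h after the dose;
- no dairy for 4 h after the dose.

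The limits to oral products and to active ingredients are needed. A bar on any product containing a multivalent cation would literally catch IV fluids and tablet excipients, which is not intended in hospitalized children on other treatment.

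The cost is amendment wording, with no added visits or samples. The only burden on a child is that a supplement is re-timed around a single dose.

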7.6 Dose Adjustments and Interruptions of Test Article

No dose adjustments or planned interruptions of test article will be permitted during this study.

7.6.1 Subject Numbering

Upon signing the informed consent and pediatric assent, the subject will be assigned a unique subject number. Subjects who have been pre-screened, but who do not sign a pediatric assent/ICF will not be assigned a subject number. A subject who discontinues participation or is withdrawn before receiving a treatment assignment, and who is re-screened at a later time will be assigned a new subject number and recorded as re-screened. Re-screening is at the discretion of the investigator and in consultation with the medical monitor. The investigator will maintain a subject master list to document every subject who has signed a pediatric assent and ICF. A copy of this list should be retained in the investigator's study files.

7.7 Dispensing Test Article

Each study site will be supplied by the sponsor with the investigational product.

7.8 Prior and Concomitant Therapy

Treatments that have been administered within the 72 hours prior to the date of informed consent and pediatric assent, or during the Screening phase, will be recorded in the eCRF. The investigator is to instruct the subject and his/her parent/LAR to notify the study site about any new medications he/she takes after the administration of the test article. All medications and significant non-drug therapies (including physical therapy and blood transfusions) administered after the subject receives treatment with test article must be listed in the eCRF (see Section 8.15).

7.9 Prohibited Therapy

All investigational medications or devices used during the 30 days prior to Screening are prohibited.

The following therapies are excluded:

- Antacids and multivitamins containing multivalent cations (e.g., aluminum, magnesium, calcium, bismuth, iron, or zinc) for 6 hours before and within 4 hours after oral doses.

7.10 Permitted Treatments

All other treatments not specified as prohibited are permitted during the study. Treatment for infection under study is at the discretion of the investigator or the subject's health care provider and will be considered as a concomitant medication.

Subjects or caregivers should be encouraged to contact site personnel before starting any new treatment.

For all treatments received by the subject during the study, relevant information must be recorded on the subject's eCRF.

7.11 Treatment Compliance

Compliance and any unresolved discrepancies will be documented in the source document and on the drug inventory record. The test article eCRF should reflect the reconciled dosing information provided by the subject charts.

7.12 Packaging and Labeling

The investigational test article, omadacycline, will be packaged by the sponsor and supplied to the investigator.

7.13 Storage and Accountability

Test article must be received at the study site by a designated person, handled and stored safely and properly, and kept in a secured location to which only the investigator and designated staff have access. Upon receipt, the test article should be stored according to the instructions specified on the drug labels. Storage conditions must be adequately monitored, and appropriate temperature logs maintained as source data.

The designated study personnel must maintain an accurate record of the shipment and dispensing of test articles in the study-specific medication accountability ledger.

